9.0 Vulnerable Populations*

If the research involves special populations that are considered vulnerable, describe the safeguards included to protect their rights and welfare.

NOTE: You should refer to the appropriate checklists, referenced below, to ensure you have provided adequate detail regarding safeguards and protections. You do not, however, need to provide these checklists to the IRB.

9.1 *For research that involves **pregnant women**, safeguards include:*

NOTE CHECKLIST: Pregnant Women (HRP-412)

Response:

N/A: This research does not involve pregnant women.

9.2 *For research that involves **neonates of uncertain viability or non-viable neonates**, safeguards include:*

NOTE CHECKLISTS: Non-Viable Neonates (HRP-413), or Neonates of Uncertain Viability (HRP-414)

Response:

N/A: This research does not involve non-viable neonates or neonates of uncertain viability.

9.3 *For research that involves **prisoners**, safeguards include:*

NOTE CHECKLIST: Prisoners (HRP-415)

Response:

N/A: This research does not involve prisoners.

9.4 *For research that involves **persons who have not attained the legal age for consent to treatments or procedures involved in the research (“children”)**, safeguards include:*

NOTE CHECKLIST: Children (HRP-416)

Response:

N/A: This research does not involve persons who have not attained the legal age for consent to treatments or procedures (“children”).

9.5 For research that involves **cognitively impaired adults**, safeguards include:

NOTE CHECKLIST: Cognitively Impaired Adults (HRP-417)

Response:

N/A: This research does not involve cognitively impaired adults.

9.6 Consider if other specifically targeted populations such as students, employees of a specific firm, or educationally or economically disadvantaged persons are vulnerable. **Provide information regarding their safeguards and protections, including safeguards to eliminate coercion or undue influence.**

Response: Students may be recruited in this study, but cable actuated training and observing their gait with sEMG sensors, reflective markers, or IMUs won't create any risks. They are allowed to stop and take breaks during the study anytime if they need it. Students will be explicitly informed that their grades in any course will not be affected, positively or negatively, based on your participation in this study

10.0 Eligibility Screening*

10.1 Describe **screening procedures** for determining subjects' eligibility.

Screening refers to determining if prospective participants meet inclusion and exclusion criteria.

Include all relevant screening documents with your submission (e.g. screening protocol, script, questionnaire).

Response: [name] is a licensed physical therapist. She will perform screening procedures for the patients. We will examine the individual's ability to ambulate 100 feet with or without assistive devices but not with the assistance of a caregiver to ensure independent walking through the protocol.

N/A: There is no screening as part of this protocol.

11.0 Recruitment Methods

N/A: This is a records review only, and subjects will not be recruited. NOTE: If you select this option, please make sure that all records review procedures and inclusion/exclusion screening are adequately described in other sections.

11.1 Describe when, where, and how potential subjects will be recruited.

NOTE: Recruitment refers to how you are identifying potential participants and introducing them to the study. Include specific methods you will use (e.g. searching charts for specific ICD code numbers, Research Participant Groups, posted advertisements, etc.).

Response: Extensive distribution of flyers through organizations such as WNY parent's network, UB boards that allow study flyers, clinical

facilities in the greater Buffalo region, and clinicians that see patients with CP. The Buffalo Research Registry (BRR) is a database of people from Buffalo and Western New York who have shown interest in becoming research study volunteers. We will ask for a list of potential participants from the BRR. A flyer providing information on the study will be emailed or mailed to potential participants from this list.

11.2 Describe how you will protect the privacy interests of prospective subjects during the recruitment process.

NOTE: Privacy refers to an individual's right to control access to him or herself.

Response: Participants will self-select to respond to one of the flyers for the study. They need to choose to contact the researchers to participate in the study. The settings for the phone conversation and data collection will be private areas. *The researcher will emphasize that participation in this study is voluntary and subjects may withdraw at any time with no consequences.*

11.3 Identify any materials that will be used to recruit subjects.

NOTE: Examples include scripts for telephone calls, in person announcements / presentations, email invitations.

 *For advertisements, include the final copy of printed advertisements with your submission. When advertisements are taped for broadcast, attach the final audio/video tape. NOTE: You may submit the wording of the advertisement prior to taping to ensure there will be no IRB-required revisions, provided the IRB also reviews and approves the final version.*

Response: *Flyers and follow-up phone conversations when participants demonstrate an interest in the study.*

12.0 Procedures Involved*

12.1 Provide a description of **all research procedures or activities being performed and when they are performed once a subject is screened and determined to be eligible. Provide as much detail as possible.**

NOTE: This should serve as a blueprint for your study and include enough detail so that another investigator could pick up your protocol and replicate the research. For studies that have multiple or complex visits or procedures, consider the addition of a schedule of events table in your response.

Response: Participants will be scheduled for an appointment to visit AWEAR (Assistive Wearable Robotics) lab which is located at University at Buffalo Furnas Hall Room 809 or Kimball 115. They will be asked to wear comfortable clothing which won't restrict their natural movement. Participants are required to wear reflective markers on the whole body to record the motion by a Vicon motion capture system. Similarly, Delsys surface electromyography sensors will be attached to the skin of the participant to record the muscle activation during walking. The instrumented insole will also be added to the participant's shoes. The participant will walk on the treadmill for 5 minutes as warming-up and 20-minutes

of training with a cable-actuated robot will be provided. The device will augment 15% of their own body weight. While they are walking with the device, auditory feedback will be provided for the participants who are assigned to the auditory group. The auditory and non-auditory groups will be randomly assigned. Furthermore, one of the 3 different types of auditory feedback will be randomly assigned to participants from the feedback group. A break of 5 minutes will be provided after 10 minutes of walking with the device. After the robotic training is completed, the device will be taken off and the participant will walk without the device to monitor the immediate retention of the training. After every 10 minutes, the researcher will ask the participant questions as per the Borg exertion scale to check the fatigue of the participant. After finishing the treadmill session, participants will take a 10-minute break and walk 4 minutes with (or without auditory feedback) on the floor. The participant will repeat overground walking for a total of three sets. There will be a total of ten training sessions, two or three sessions a week and each session will last for a maximum of 3 hours. In addition, pre and post-training visits are required to evaluate functional gait assessment, 6-min-walk, leg strength using a dynamometer, international physical activity questionnaire (short form), usability questionnaire, and Modified Ashworth test by a physical therapist.

12.2 Describe what data will be collected.

NOTE: For studies with multiple data collection points or long-term follow up, consider the addition of a schedule or table in your response.

Response:

- We will schedule the participants to visit the lab. We will make a table when the participants are available.
- *EMG data from the muscles*
- *Vicon motion capture data*
- *Photo and Video of the test*
- *IMU sensor data*
- *Smart insole data*
- *Ground reaction force*

12.3 List any instruments or measurement tools used to collect data (e.g. questionnaire, interview guide, validated instrument, data collection form).

Include copies of these documents with your submission.

Response: Vicon motion capture system, Delsys Trigno sEMG system, and Bertec Force plate instrumented treadmill, Smart Insole

12.4 Describe any source records that will be used to collect data about subjects (e.g. school records, electronic medical records).

Response: N/A

12.5 *Indicate whether or not **individual** subject results, such as results of investigational diagnostic tests, genetic tests, or incidental findings will be shared with subjects or others (e.g., the subject's primary care physician) and if so, describe how these will be shared.*

Response: N/A

12.6 *Indicate whether or not **study** results will be shared with subjects or others, and if so, describe how these will be shared.*

Response: The data and study results will be not shared with the subject.

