Deterioration of locomotion skills is a major problem in persons with CP. This can lead to a sedentary lifestyle at an early age and a significant decrease in the quality of life [4]. A few studies have addressed progressive resistive strength and aerobic training in adults with CP which show significant strength improvements in their walking ability and gait parameters [5]. As an extension of these studies, we investigated the use of targeted gait training using a cable-actuated system over a treadmill that promoted strengthening during walking in children with CP [6]. This cable-actuated system provided downward force and participants had to extend their legs against the force while walking on a treadmill. This leads to a straighter walking posture, longer stride, and reduced toe-walking pattern in a supervised environment. Once the participants were taken out of the actuated cable system, they showed immediate improvement of knee extension and heel-to-toe walking. This is because participants recalibrated their movement to walk against the downward force and its effect lasted for a while after the force was removed. This after-effect of adaptation may be used in physical therapy to let the patients experience a more normal movement pattern [7]. In the proposed study, we will introduce the use of instrumented insoles to provide feedback to sustain positive after-effects in unsupervised ecological environments. Sensory feedback has been shown to improve the gait features of individuals with cerebral palsy in the past [8, 9, 10]. We will use similar methods to assist adults with CP to retain the positive motor adaptation from using the cable-actuated system on the treadmill. We will collect pressure data, foot clearance, heel-to-toe pattern from smart insoles and provide feedback to the participant on their gait pattern. We

hypothesize that once participants have experienced gait in response to resisted gait training, the feedback from the insoles will assist them to maintain the improved gait. Furthermore, we hypothesize that the use of sensory feedback with minimal supervision will lead these individuals to take an active role in their gait training. It can foster collaboration between the therapist and participant in the shared goal of improved gait quality. These are essential components of self-management, especially important for individuals with chronic conditions like cerebral palsy.

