The goal of the suggested work is to retain the positive after-effects of resistive gait training for longer periods using sensory feedback until it becomes the normal gait pattern by repeated and reinforced training. For the first time, we will examine the feasibility of using sensory feedback to reinforce the adaptation from the resisted gait training. Previous robotic devices focused on the adaption itself during the training, but methods on sustaining the adaptation after the training have not been well studied, despite the significance of maintaining the adaptation. Different types of auditory feedback will be explored using the data from smart insoles to extend the carry-over effect of motor adaption during training. The knowledge of this study can be widely used in other rehabilitation devices to sustain and maximize the training effect. Secondly, this approach creates a rehabilitation platform that includes both supervised and unsupervised training which can lead to the participant taking a more active role in their care. Once participants step off the treadmill, they will use the instrumented insoles and the sensory feedback to maintain positive gait changes from the gait-resisted training. By suggesting a training method collaborating in-clinic, we envision a successful therapeutic intervention that is tailored to the needs of an adult with CP. It provides in-clinic gait resisted training to safely provide a stimulus that can alter their gait. The proposed study would also create a rich biomechanical data set over the whole gait cycle of adults with CP. Since this is an understudied population, this information would be invaluable to clinicians and researchers. This data set will help to understand neuromechanical characteristics of the gait of adults with CP for future implications in physical and pharmacological interventions, and as the long-term mission to promote healthy aging in the population with cerebral palsy by improving their functional mobility.

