5.0 Study Design*

5.1 *Describe and explain the study design (e.g. case-control, cross-sectional, ethnographic, experimental, interventional, longitudinal, observational).*

Response: The experiment protocol involves a maximum of ten sessions and will take two or three hours for each session. Baseline data will be collected before the first session for both overground and treadmill walking. During this session, the sound level will be adjusted based on the feedback received from the users. The researcher will ask the comfortable sound level to the participant before starting the experiment. Training will be conducted on the treadmill with the cable-actuated device for about 20 minutes. When the cables were removed, participants walked on the treadmill for 4 minutes during the post-training session. During training and post-training, participants will be exposed to feedback while walking on the treadmill. After treadmill walking, CP participants will be asked to take a ten-minute break and then practice overground walking for two minutes with auditory feedback (type A) and without it (type B). Effects of 3 different types of

auditory feedback will be explored namely, rhythmic sounds, movement sonification, and sound notifying erroneous gait. Group A participants will be further divided into groups depending on the type of auditory feedback that will be provided. Participants will participate in a maximum of 10 sessions, two or three times a week. Before the first and after the last training, participants will be evaluated for functional gait assessment, 6-min-walk, leg strength using a dynamometer, international physical activity questionnaire (short form), usability questionnaire, and Modified Ashworth test by a physical therapist.

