Furthermore, using the data from the smart insole and Bertec Force plate instrumented treadmill, three different types of auditory feedback will be provided to the selected participants. The sound level of the auditory feedback is adjustable and will be determined based on the user's feedback during the baseline trials. Rhythmic auditory feedback will be generated to provide participants information about the cadence which will help them synchronize their footsteps. Another type of auditory feedback consists of, an unpleasant sound which will be generated in case the gait characteristics such as knee flexion or ankle plantarflexion of the participants abnormal. The last type of auditory feedback will comprise modulating the characteristics such as pitch and tempo of the sound to reflect the motion of the lower limbs[5]. Analyzing the effects of these different types of auditory feedback will not only allow us to identify if auditory feedback aids in the retention of benefit from strength training for a longer duration but also identify the varying degrees of effects of different types of auditory feedback on retention of gait adaptations from cable actuated robot.

- [1] J. Kang, D. Martelli, V. Vashista, I. Martinez-Hernandez, H. Kim, and S. K. Agrawal, "Robot-driven downward pelvic pull to improve crouch gait in children with cerebral palsy," *Sci. Robot.*, 2017, doi: 10.1126/scirobotics.aan2634.
- [2] Yang, Zhuolin, et al. "A smart environment-adapting timed-up-and-go system powered by sensor-embedded insoles." *IEEE Internet of Things Journal* 6.2 (2018): 1298-1305.
- [3] Yang, Zhuolin, et al. "A smart environment-adapting timed-up-and-go system powered by sensor-embedded insoles." *IEEE Internet of Things Journal* 6.2 (2018): 1298-1305.
- [4] Instrumented Treadmills, URL:- <https://www.bertec.com/products/instrumented-treadmills>
- [5] Schaffert, Nina, et al. "A review on the relationship between sound and movement in sports and rehabilitation." *Frontiers in psychology* 10 (2019): 244.

6.1 Drug/Device Handling: If the research involves drugs or device, describe your plans to store, handle, and administer those drugs or devices so that they will be used only on subjects and be used only by authorized investigators.

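### After baseline, the plan specifies no cables-off gait or sEMG recording away from the same-day after-effect, so as written retention is supported only for minutes, with feedback on in the auditory group

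*Combined protocol and SAP*

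**What the plan says.** **Aim.** Section 4.1 says the work is meant to "retain the positive after-effects of resistive gait training for longer periods using sensory feedback until it becomes the normal gait pattern". Section 6.0 expects the analysis to "identify if auditory feedback aids in the retention of benefit from strength training for a longer duration". Hypothesis 2 (section 2.2) says that feedback will reinforce retention and gives no time horizon.

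**Gait recordings.** Section 3.0 names motion and sEMG during walking as the two primary outcomes, without time points. Section 5.1 states: "Baseline data will be collected before the first session for both overground and treadmill walking". After each training bout, 5.1 has a 4-minute treadmill walk with the cables off. Section 12.1 describes that walk as one in which "the participant will walk without the device to monitor the immediate retention of the training". Overground walking follows a 10-minute break.

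**Sound during these walks.** Section 5.1 exposes participants to feedback during the post-training treadmill walk. Sections 5.1 and 12.1 have the overground walk done with or without feedback.

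**Before training.** Section 12.1 fits markers, sEMG and insoles and then says: "The participant will walk on the treadmill for 5 minutes as warming-up". It does not say whether that walk is recorded.

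**Post-training visit.** Section 12.1 says: "In addition, pre and post-training visits are required to evaluate functional gait assessment, 6-min-walk, leg strength using a dynamometer", followed by questionnaires and the Modified Ashworth test. Motion capture and sEMG are not listed and the visit has no date. Section 13.2 gives no follow-up time.

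**Analysis.** Section 19.1 proposes a mixed model with time within day, feedback, day and assignment. Its main statistic is improvement from baseline to the end of treatment.

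**The concern.** Section 4.1 says of the adaptation to the cable force that "its effect lasted for a while after the force was removed". A walk recorded shortly after the cables come off can therefore contain that day's transient response as well as anything kept from earlier sessions. Retention over days needs a measurement taken before the next bout of cable training, or on a separate day. The plan does not assign one.

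Two conclusions are at stake. For Hypothesis 2, the comparison of auditory and non-auditory groups would describe the first minutes after unloading, and would compare people walking with sound against people walking without it. For Hypothesis 1, a baseline-to-end gait contrast could credit ten sessions with a response that one session can produce. Between-session values that are not recorded at the time cannot be recovered later.

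**Working it through.** The plan gives no figure for how long retention is followed, so there is none to reproduce. Section 19.2 mentions six repeated measures but does not say when they are taken.

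**1. Time from cable removal to the end of the last described walk**

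Inputs: treadmill walk 4 min (5.1; 12.1 gives no length); break 10 min (both sections); overground walking 2 min (5.1) or three sets of 4 min (12.1). Rest between sets is not stated.

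| Reading | Sum | Minutes |
|---|---|---|
| 5.1, one 2-minute walk | 4 + 10 + 2 | 16 |
| 5.1, if each person walks with and without sound | 4 + 10 + 2 + 2 | 18 |
| 12.1, three sets, no rest between | 4 + 10 + 3 × 4 | 26 |
| 12.1, break repeated before each set | 4 + 3 × (10 + 4) | 46 |

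**2. Time between sessions**

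Two or three sessions a week give a mean gap of 7/3 = 2.3 to 7/2 = 3.5 days. Ten sessions have 10 − 1 = 9 later starts, so a recorded warm-up would give up to nine between-session values per person.

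**3. What each contrast contains**

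For session k, write B for baseline, C(k) for change carried over to the start of the session, A(k) for that day's after-effect, and S for the effect of walking with sound on (auditory group only).

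- Warm-up, cables and sound off: B + C(k).
- Post-cable walk: B + C(k) + A(k), plus S in the auditory group.
- Session-10 post-cable walk minus baseline: C(10) + A(10), plus S in the auditory group.
- Group difference on a post-cable walk: difference in C + difference in A + S.
- Group difference on a warm-up: difference in C alone, which is between-session retention.

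A day term fitted only to post-cable walks takes in changes in both C(k) and A(k). It isolates C(k) only if A(k), and S where present, stay the same from session to session. The plan does not state that assumption.

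**4. Precision of one later visit (bears on the optional part of the fix)**

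Take 10 per group and the effect size of 0.5 from 19.2. Assume that effect is in SD units of a single measurement, and use a two-sided 5% test.

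- Standard error = √(2/10) = 0.447.
- Power ≈ Φ(0.5/0.447 − 1.960) = Φ(−0.842) = 20%.
- Effect detectable with 80% power = (1.960 + 0.842) × 0.447 = 1.25 SD.
- Size for 80% power at 0.5 = 2 × 2.802² / 0.5² = 62.8, so 63 per group.
- Adjusting for baseline at an assumed correlation of 0.3 to 0.7 multiplies the SD by √(1 − r²). Power is then 22% to 35%, and 58 to 33 per group are needed.

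**The case against.** A reader might infer that gait is measured only at baseline and in the half hour after unloading, so that the trial cannot separate lasting change from the after-effect. The documents do not support that. Sensors are on before the warm-up, and nothing says the warm-up goes unrecorded. Section 19.1 models day and time within day, which implies several recordings per day on several days. If a pre-training walk is one of them, the model can separate the two components. Section 3.0 also says the pre/post evaluation will show kinematic and kinetic changes. None of the listed tests measures kinematics, but the sentence leaves motion capture at that evaluation open.

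A reader might also infer that the Objective 1 result is necessarily contaminated. Section 19.1 does not tie the end-of-treatment value to the session-10 post-cable walk. The functional gait assessment and 6-minute walk address walking ability and are placed at a separate post-training visit.

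Three further points have weight. Hypothesis 2 sets no horizon, and longer may mean longer than without feedback. Both groups receive the same cable training, so the after-effect alone does not invalidate a comparison of immediate retention. This is also a pilot.

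These arguments limit the point to what the plan leaves unspecified. They do not supply a pre-training, sound-off recording or a contrast that uses one, and they do not remove the sound-on difference between groups. Sections 4.1 and 6.0 still set an aim beyond immediate retention.

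**Conclusion.** The point holds in a limited form. As written, no section specifies a cables-off, feedback-off gait or sEMG recording before training at sessions 2 to 10 or at a dated post-training visit, and no contrast uses one. The described post-training walks end about 16 to 26 minutes after unloading, or about 46 if the break is repeated, while sessions are on average 2.3 to 3.5 days apart. Following the text gives a retention comparison that is immediate and partly cued.

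The mixing of accumulated change with the same-day after-effect in the baseline-to-end contrast is conditional: it arises if a post-cable walk is the end-of-treatment value. The timings apply the 4-minute treadmill walk of 5.1 to the 12.1 schedule. The reading of sound as on relies on 5.1 for the treadmill walk and on both sections for the overground walk. The documents give no size for the after-effect or its decay, so no bias in outcome units can be calculated.

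**What to change.** 1. **Section 12.1:** state that a fixed segment of the existing 5-minute warm-up, for example the last minute, is recorded at every session (motion, sEMG, insoles) with cables and sound off in both groups.
2. **Section 19.1:** make the group comparison of these start-of-session values over sessions 2 to 10, adjusted for the session-1 baseline, the between-session retention contrast for Hypothesis 2.
3. **Section 19.1:** define the end-of-treatment gait value as a pre-training or separate-day recording, not a post-cable walk. A session-10 warm-up reflects nine completed sessions; only a later day reflects all ten.
4. **Labels and conclusions:** keep the post-cable walks as the immediate after-effect, say whether sound was on, and limit the retention conclusion to the interval measured.
5. **Optional:** date the existing post-training visit and add a short cables-off, sound-off motion and sEMG recording. Report it as an estimate with its interval, because power at 10 per group is low.
6. **Reconcile 5.1 and 12.1** on overground walking (2 minutes versus three sets of 4 minutes).

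Items 1 to 4 need protocol wording and the recording and processing of a walk that already takes place with sensors fitted. They add no participants or visits. Item 5 makes one visit longer because of sensor set-up.
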